Adequacy of Sample Size: Optimal Design 2.0 Software⁵³ was used to conduct power analyses for hierarchical linear modeling (see C3) of treatment effects. An alpha level of .05 was chosen for each of the primary hypotheses. Given that our pilot research has found medium effect size (ES) on the higher end of the continuum for PTSD severity and medium ES for re-abuse severity (see C1), a more conservative medium ES (delta = .60; which is on the lower end of the continuum of medium effect sizes) was assumed in an effort to account for the potential for reduced effects in the current study. We also assumed an ES variability of .07 across the 6 shelters where recruitment will occur. An ES variance of .07 corresponds to a standard deviation of approximately .2, which for ES = .60 reflects substantial variation in treatment ES across shelters. Thus, we are powering the study to be able to detect a medium ES, even if there is substantial ES variability across shelters. Additional assumptions for the power analysis included a proportion of explained variance by the blocking variable (i.e., shelter) of .1 and a proportion of explained variance by the level 1 covariate (i.e., baseline PTSD or violence severity), of .3. There is little literature on which to base estimates of these two parameters for the proposed study, but these parameters have relatively little effect on sample size requirements given the specified ES, ES variability, and number of shelters. For example, the most extreme value of 0 (instead of .1) for the proportion of explained variance by the blocking variable would only increase the necessary sample size by 2 per shelter. Also, even an extreme value of .1 (instead of .3) for proportion of explained variance by the baseline level of the outcome variable would only increase the necessary sample size by 5 per shelter. Using the parameter estimates specified above and a desired power of .80, results of the

power analysis indicated that 25 participants were required per shelter for a total N of 150. In our pilot research we had retention rates of 81-95% (see C1). Thus, assuming the more conservative attrition rate of approximately 20%, we would need 31 participants per shelter, for a total of 186 participants to achieve a power of .80 to detect medium-sized treatment effects for our primary outcomes.

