
Assessment: Participants will be assessed at six primary time points: (1) baseline, (2) 1-week post-shelter (PS) treatment (tx), (3) 1-week PS, (4) 1-week post-tx (i.e., 13 weeks PS), (5) 6-months post-tx, and (6) 1-year post-tx using a combination of well-known structured interviews and self-report questionnaires with demonstrated reliability and validity. For data and safety monitoring purposes (see E2), participants will also complete an abbreviated assessment designed to assess for clinical deterioration and re-abuse at mid-shelter tx (i.e., 5 weeks after begin tx), mid-PS tx (i.e., 6-weeks PS) assessment, and 3- and 9-months post-tx (see Table 1). Assessment procedures will mirror those that have been successful in our pilot work with HOPE. While women are residents of the shelter, assessments will take place at the shelter. Follow-up assessments will occur at the safest and most convenient location for the women (e.g., hospital, public library, in-home visit). In the event that a participant cannot attend a follow-up assessment in person (e.g., moves out of state) interviews will be conducted via phone. Three blind research assistants will conduct all follow-up assessments, under the supervision of the project coordinator. The RAs will be trained in the administration of all interviews and research procedures. This training will include strategies for the accurate assessment of PTSD and IPV using training procedures already in place in [name] research lab. A minimum of 80% agreement on all ratings will be required to establish inter-rater reliability. The RAs will be blind to treatment condition, as well as to the study design and hypotheses. Table 1 contains a summary of measures given at each assessment period. All measures will be administered electronically with software available from Questionnaire Development System (QDS). Self-report measures will be administered with the Audio Computer Administered Self Interview (ACASI) module, and all interviews will be administered with the Computer Assisted Personal Interview (CAPI) module. We chose to use ACASI to increase women's likelihood of disclosing stigmatized experiences, to streamline data entry, and to improve data reliability.

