at intake will be updated and new releases will be obtained as necessary. We will also collect information regarding community resources (i.e., social services, primary care physicians) with whom the women may be involved and permission to contact these agencies in order to locate participants. When we are unable to contact women by phone, letters and outreach will be used to schedule follow-ups. Additionally, women will receive appointment cards with all details regarding their next appointment. The women will also be provided pens and keychains at each time point that include our research number. Also, child-care and bus passes will be provided whenever necessary. Finally, financial incentives will be built into the study in the form of participant fees to be paid upon completion of all post-shelter and follow-up assessments. Financial incentives designed to reimburse women for childcare and transportation costs for sessions that occur outside of shelter will also be provided. Additionally, as women may eventually return to an unsafe environment (i.e., back to their abuser), safe methods of contact will be negotiated at each stage described above and participants will be encouraged to contact the research team if they feel that contact at any location is no longer safe (see E1).

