Prior to conducting analyses for the main project aims, a series of routine procedures will be conducted to ensure the data accuracy/adequacy. We will also examine the distribution of our key variables for skewness, variability, missing data, and outliers. Data will be transformed to achieve normality if needed. At this time, we will also assess the effectiveness of the randomization procedures. If between-group differences exist, relevant variables will be included as covariates in outcome analyses. We will also explore whether contamination is a significant issue by comparing members of the control groups reporting they were exposed to specific HOPE content to those who were not exposed to determine if such exposure impacts outcome, and control for exposure in analyses below if necessary. Although only a small percentage of participants in our pilot work reported initiation of a new medication (3.3%), change in dose or type of ongoing medications (3.3%), or cessation of a medication (5%), we will also explore whether medication changes during treatment impacted outcome, and control for medication changes in analyses if necessary (see below). Additionally, we will preliminarily investigate therapist effects on attendance, attrition, and primary outcomes and use this data to inform future research with HOPE that will more directly assess therapist effects. Finally, pattern mixture methods^{74, 75} will be used to assess the ignorability of missingness in all outcome analyses described below. All analyses will include an intent-to-treat analysis (using data from all randomized participants) and a minimal attendance analysis (i.e., attending at least $\frac{1}{2}$ of sessions). For intent-to-treat analyses, missing data will be handled using multiple imputation with an expectation maximization algorithm.

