Primary and Secondary Outcomes: Hierarchical linear modeling (HLM) will be used to analyze the different trajectories that may occur between the two treatment groups. Separate HLMS will be conducted for all primary outcomes (i.e., PTSD and re-abuse severity), as well as for each secondary outcome. Additional time-varying (e.g., medication changes measured at multiple time points) and time-invariant covariates (e.g., length of shelter stay) that might explain additional variability in symptom level and change can also be modeled. Additionally, using the procedures described by Jacobson and Traux⁷⁶, the reliable change index will be computed for primary outcomes at 1-week post-treatment in order to assess whether the change in PTSD symptoms experienced by HOPE participants was clinically meaningful. Exploratory analyses will also be conducted to determine what constitutes an adequate dose of HOPE.

Other Secondary Outcomes: Mixed design ANOVAs will be used to analyze treatment effects for attentional biases and cortisol reactivity. Cortisol reactivity will be assessed by analyzing the area under the curve (AUC) of the reactivity curve. This will be computed in two ways: area under the curve with respect to increase (AUC_i) and area under the curve with respect to ground (AUC_G)⁷⁷. Mixed design ANOVAs that include a between-subjects factor (treatment group) and within-subjects factor (assessment time point) will be used to compare

both AUC_i and AUC_G values at each of the three time points as a function of treatment group. To evaluate treatment effects on attentional biases, we will conduct mixed design ANOVAs that include a between-subjects factor (treatment group) and within-subjects factors (e.g., word type; assessment time point). A group X word type X assessment time point interaction will be tested and deconstructed to determine, for example whether HOPE participants show reduced (relative to controls) attentional interference (i.e., less difficulty disengaging attention) to trauma-related stimuli (but not other types of stimuli) following treatment.

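### Pattern mixture comparisons cannot establish that missingness is ignorable, and the plan has no analysis showing how far the primary conclusions depend on missing at random

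*Combined protocol and SAP*

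**What the plan says.** Section C3 (Data Analytic Plan) has two sentences on missing outcomes. Pattern mixture methods "will be used to assess the ignorability of missingness in all outcome analyses described below". For the intent-to-treat analyses, "missing data will be handled using multiple imputation with an expectation maximization algorithm". The section defines no dropout patterns, test, threshold, identifying restriction or shift for unseen values, and it does not say what follows from the assessment. The other planned version of each analysis, restricted to women who attended at least half the sessions, selects on attendance and does not probe missing outcomes.

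The outcome model comes next in C3: "Hierarchical linear modeling (HLM) will be used to analyze the different trajectories that may occur between the two treatment groups". Under Assessment in C2, "Participants will be assessed at six primary time points". Table 1 adds four shorter assessments at which the DTS and CTS-2 are also collected: mid-shelter treatment, mid-post-shelter treatment, and 3 and 9 months post-treatment.

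On expected loss, Adequacy of Sample Size in C2 says: "assuming the more conservative attrition rate of approximately 20%, we would need 31 participants per shelter, for a total of 186 participants". Retention in C2 recognises that some women may go back to an unsafe home and says that "participants will be encouraged to contact the research team if they feel that contact at any location is no longer safe".

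**The concern.** Ignorability is a statement about the values nobody saw, given those that were seen. Adding dropout-pattern terms to a model of the observed data shows whether women who leave had different observed trajectories from those who stay. That is closer to a test of missing completely at random (MCAR). A pattern mixture model speaks to MNAR only once the analyst supplies a restriction or a shift for the unseen values, and C3 supplies neither.

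The gap matters here because loss could be tied to the outcome. Re-abuse severity is a primary outcome, and a woman who returns to the abuser may be harder to reach. C1 reports that 83% of the first pilot sample had further IPV, contact with the abuser and/or another significant trauma after leaving shelter. Loss may also exceed 20%. The 80% retention in the expanded-HOPE pilot was at 9 months post-shelter, whereas the last visit here is 1 year after a treatment that ends about 3 months post-shelter, so at about 3 + 12 = 15 months. Readers of the results would have a statement about ignorability that the data cannot support, and no view of how the two primary conclusions move if MAR fails.

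**Working it through.** **1. The plan's own figure.** C2 gives no number for the missingness check, so the figure to reproduce is the sample size. Its settings are "An alpha level of .05 was chosen for each of the primary hypotheses" and "Using the parameter estimates specified above and a desired power of .80". Inputs from the same paragraph: J = 6 shelters, effect .60, effect variance v = .07, B = .1 explained by shelter, R² = .3 explained by baseline. With n = 25 per shelter:

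λ = J × .60² / (v + 4(1 − B)(1 − R²)/n) = 2.16 / (.07 + 4 × .9 × .7 / 25) = 2.16 / .1708 = 12.6

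The noncentral F on 1 and 5 degrees of freedom gives power .809, and 25 is the smallest n that reaches .80, so 150 reproduces. For attrition, 150/.8 = 187.5 against the stated 186, and 186 × .8 = 148.8. Planned missingness at about 20% is therefore built into the design.

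**2. What a pattern check detects.** From the documents: 186 women 1:1, six visits, about 20% dropout, effect .60. Assumed: residual variance .49, random-intercept variance .49, random-slope variance .36, and dropout log-odds rising 1 or 2 per unit of whatever drives dropout. There were 400 trials per setting (Monte Carlo error at most about 2.5 points), fitted by generalised least squares with known covariance. The check was a 5% Wald test of completer/dropout terms crossed with time and arm. The true treatment-by-time coefficient is −.60. Where two values appear, they are for log-odds slopes 1 and 2.

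| Dropout mechanism | All four pattern terms fire | Pattern × arm terms only | Error in treatment × time from the MAR model |
|---|---|---|---|
| MCAR | 5.2% | 5.0% | −.002 |
| MAR on last observed value, same in both arms | 98.5%, 100% | 3.7%, 3.5% | +.001, −.008 |
| MAR, opposite direction by arm | 100%, 100% | 99.3%, 99.8% | +.005, +.011 |
| MNAR on unseen current value, same in both arms | 73.8%, 97.0% | 3.3%, 4.5% | +.035, +.060 |
| MNAR on unseen current value, opposite by arm | 75.7%, 99.3% | 75.5%, 93.8% | −.143, −.210 |
| MNAR on latent slope | 20.3%, 27.5% | 6.0%, 4.8% | +.002, −.008 |
| MNAR on occasion-specific unseen part, same in both arms | 4.0%, 4.3% | 5.2%, 3.0% | +.003, −.001 |
| MNAR on occasion-specific unseen part, opposite by arm | 5.5%, 5.5% | 6.0%, 5.5% | −.038, −.069 |

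Interval coverage was 94–98% in the MAR rows and fell to 78% in the worst MNAR row. The alarm does not track the bias. It is near certain in valid MAR rows and nominal in one biased row. Testing only the pattern × arm terms removes the MAR alarm when both arms share a mechanism, but then also misses the +.035 to +.060 error.

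A second set of assumptions (variances .55, .0008 and .45; visits at months 0, 2, 2.25, 5, 11 and 17) gave the same picture at lower rates. With dropout log-odds rising .4, .7 or 1.0 per SD, the four-term check fired in 32%, 86% and 99% under MAR and in 18%, 42% and 79% under MNAR on the current value. In that last case the 1-year treatment-effect bias was at most about .025 SD.

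**3. Size of bias.** Let p be the fraction lost in an arm and δ the amount by which unseen values are worse than MAR predicts. The arm's complete-data mean is its MAR mean plus pδ, so:

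true benefit − MAR benefit = p(PCT) × δ(PCT) − p(HOPE) × δ(HOPE)

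With a common δ of 1 SD:
- Loss 20% and 20%: .20 − .20 = 0.
- Loss 27% PCT and 13% HOPE (mean 20%): .27 − .13 = +.14, so MAR understates the benefit. Simulation gave .59 from the HLM against a complete-data .73.
- Loss 13% PCT and 27% HOPE: −.14, so a MAR estimate of .60 would stand against a truth of .46.

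With equal 20% loss but a 1 SD shift in HOPE only: 0 − .20 × 1 = −.20, so .60 would become .40. The 1 SD shift and the loss splits are assumptions. The documents give only the overall rate.

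**The case against.** Four points can be made for the plan.

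First, C3 says the methods will assess ignorability. It does not say that a decision hangs on the result, that imputation will stay at MAR whatever is found, or that imputation parameters are fixed at their EM estimates. Pattern mixture models are also the right family for a sensitivity analysis, the wording does not exclude shifted or pattern-averaged estimates, and the two references cited there cannot be consulted here. All of this stands, but no shift or restriction is prespecified, and the purpose that is stated is one the data cannot serve.

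Second, a reader might infer that the check always alarms under MAR and is always silent under MNAR. The table does not support that. When loss depends on the unseen current value, the four-term check usually fires, and the MAR alarm rate depends on which terms are tested. The defensible statement is that the check cannot discriminate.

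Third, a reader might infer from the Retention section that contact ends once it is unsafe, making MNAR loss likely. The section says instead that safe ways of making contact are negotiated at each stage, alongside letters, outreach and agency contacts, and C2 allows telephone interviews. With CTS-2 and DTS at ten time points, re-abuse before loss may well be observed. A link between loss and re-abuse is plausible; the documents do not show it. The 83% figure came from women who were still reporting.

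Fourth, the bias may be nil. With equal loss and a common shift it is zero, and with more loss in PCT it works against HOPE. The simulations also treat a continuous score and do not cover the re-abuse count. This stands, and it is why no single bias figure should be attached to the trial.

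**Conclusion.** The concern holds in this form: the step is given a task that observed data cannot perform, and nothing else in the plan shows how the CAPS and re-abuse conclusions depend on MAR. That observed data cannot separate MAR from MNAR needs no simulation; the firing rates illustrate it and rest on assumed variances, dropout strengths and pattern terms. The size of any bias is not determined by the documents. At 20% average loss and a 1 SD common shift it runs from about zero (equal loss) to about .14 SD either way (27% versus 13%). Arm-specific shifts can produce bias even with equal loss. A reader might infer that the planned result will be biased by about .14 SD; the documents give no arm split and no shift, so they do not support that. The plan should be changed on this point, but the main intent-to-treat approach can stand.

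**What to change.** In C3:

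1. State MAR as the primary assumption for the intent-to-treat HLM and multiple imputation.
2. Specify the imputation model: arm, shelter, baseline values, and the DTS and CTS-2 scores already collected at the mid-treatment, 3-month and 9-month visits. State that imputation parameters are drawn rather than fixed at the EM estimates, since the present wording leaves this open.
3. Replace the ignorability assessment with a prespecified delta-adjusted pattern mixture sensitivity analysis for CAPS and re-abuse severity. For example, shift imputed CAPS values by 0 to +1 SD, varied separately by arm. For re-abuse use a scale suited to a count, such as a multiplicative shift.
4. Report, for each primary outcome, the shift at which the conclusion changes, together with loss by arm and visit.

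Cost: SAP wording and some analysis time. It needs no new data or participants, and the sample size is unchanged.

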
Drs. [name] and [name] have previously collaborated in a study investigating salivary cortisol levels in IPV victims⁴⁵. Using similar methodology as proposed here in which 4 salivary samples were collected over a 1-hour period (see C2), the cortisol awakening response was investigated in a sample of 52 shelter residents. Results suggested that IPV-related PTSD severity was associated with significantly greater cortisol output the first hour after waking. Thus, pilot data support the use of cortisol response within S-IPV victims as well as the ability of the research team to successfully collect multiple saliva samples from shelter residents.

C2. Study Design: To test our hypotheses that HOPE will significantly reduce severity of IPV-related PTSD and re-abuse in S-IPV victims compared to PCT, we plan to enroll 186 residents of battered women shelters with IPV-related PTSD into a prospective randomized controlled trial comparing HOPE to a attention-matched control condition (i.e., PCT). Residents of battered women shelters meeting study eligibility (see below) will be randomized into one of the two study arms. Participants will be offered 16 sessions of therapy (see Figure 1), either HOPE or PCT, beginning while women are in shelter (0-10 sessions) and continuing until 3-months post-shelter (6-16 sessions). The number of sessions attended within the shelter environment is dependent on participants' length of shelter stay, with a maximum of 10 sessions in shelter. Participants will then complete the remaining 6-16 sessions of HOPE outside of shelter. Therapy sessions will occur in shelter or another convenient, safe, and confidential location. Participants will be blinded to whether or not they received the investigative treatment or control condition. Blinded outcome assessments will be administered 1-week post-shelter treatment, 1-week post-shelter, and 1-week, 6-months, and 1-year-post-treatment.

Figure 1. Proposed model for delivery of treatment and assessment of outcome.

*Participants who are still in shelter after their 10th session will participate in monthly booster sessions.

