Rationale for the study design: Pilot work with HOPE has determined that HOPE is associated with improved outcomes relative to standard shelter services alone. Given that there is no other existing PTSD treatment appropriate for this population that could serve as a comparison condition the next logical stage in evaluating the efficacy of HOPE is to determine if HOPE offers improvement over a credible control condition that controls for the nonspecific components of therapy. PCT (see appendix) is a problem-focused, supportive therapy that is frequently used as an attention-matched control condition in clinical trials of PTSD^{46, 47}. PCT does not incorporate any of the hypothesized active ingredients of HOPE (e.g., cognitive-restructuring, acquisition of new behavioral skills, safety planning, access to resources, and empowerment strategies), but does provide psychoeducation on PTSD. Further, PCT is also clinically realistic, as many practitioners incorporate this approach into their standard practice⁴⁸. Therefore, we chose to compare HOPE to PCT, in order to determine if components specific to HOPE are responsible for observed effects, rather than nonspecific factors consistent with supportive therapy. [name] who has established expertise in PCT⁴⁶ will assist in adapting PCT to meet the needs of the proposed study, as well as in the training and supervision procedures for the PCT arm of this study.

Sample and recruitment: Participants will be 186 women recruited over 27 months from six battered women's shelters in five different counties within a 55 mile radius of the University of Akron (see letters of support) and randomized either to receive HOPE ($n = 93$) or PCT ($n = 93$). Both treatments will start while women are residents of shelter and extend after they leave shelter. Given that the length of shelter stay is variable and outside of experimenter control, session frequency will be individualized based on length of shelter stay. We are currently employing this model in our work with HOPE with success (see C1). Participants in both treatment conditions will receive up to ten individual sessions while in shelter, and 16 sessions in for up

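### The reliable change index is framed around HOPE participants, and no comparison with PCT is specified

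*Combined protocol and SAP*

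**What the plan says.** In C3, under Primary and Secondary Outcomes, "the reliable change index will be computed for primary outcomes at 1-week post-treatment", and the reason given is "in order to assess whether the change in PTSD symptoms experienced by HOPE participants was clinically meaningful". No PCT rate, between-arm difference, test or interval is attached to it.

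Three other statements bear on how this should be read:

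- The same paragraph opens with the efficacy analysis: "Hierarchical linear modeling (HLM) will be used to analyze the different trajectories that may occur between the two treatment groups".
- The opening paragraph of C3 sets the analysis populations: "All analyses will include an intent-to-treat analysis (using data from all randomized participants"), alongside a minimal attendance analysis.
- The rationale in C2 says that PCT was chosen "in order to determine if components specific to HOPE are responsible for observed effects, rather than nonspecific factors consistent with supportive therapy".

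Table 1 schedules the CAPS, DTS and CTS-2 at 1 week post-treatment with no restriction by arm.

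**The concern.** The trial is built to give a between-arm answer, but the stated purpose of the index is a within-arm question. Women must meet CAPS criteria for IPV-related PTSD to enter, so some regression to the mean is expected. PCT is a supportive therapy that includes education about PTSD, so improvement from nonspecific contact is also plausible. The share of HOPE women who pass a reliable-change threshold would contain both, together with whatever HOPE adds.

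The omission does not read like shorthand. In the next paragraph of C3, the attentional-bias analysis states outright that HOPE participants are to be set against controls. The sentence on the index has no such wording.

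What is at stake is interpretation. C3 names no other responder-type analysis, so this percentage is likely to be quoted as the clinical benefit of HOPE. The closing section aims to package HOPE for use on a large scale. A percentage without its control counterpart would not support that use.

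**Working it through.** **Plan's own figures.** The plan states no figure for the index. The one relevant input is the effect size of .60 in Adequacy of Sample Size (C2). That calculation reproduces. With 6 shelters, effect variance .07, shelter variance share .1, baseline R² .3 and 25 women per shelter, the noncentrality is 6 × .60² / [.07 + 4(.9)(.7)/25] = 2.16 / .1708 = 12.6. On F(1, 5) at alpha .05 this gives power .81, and 25 is the smallest sufficient number per shelter. So .60 SD is a fair statement of the effect the plan expects.

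**Assumed, not in the documents.** CAPS reliability .8 to .9; baseline-to-post correlation r of .3 to .7, with √.3 = .55 as the middle value suggested by the plan's R²; mean PCT improvement m of 0 to 1.0 SD; normal scores with equal SDs.

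**Formulas, in SD units.**

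- Reliable-change threshold: 1.96 × √[2(1 − reliability)]. At .9 this is 1.96 × √.2 = .88. At .8 it is 1.96 × √.4 = 1.24.
- SD of change: √[2(1 − r)]. At r = .55 it is .95.
- PCT rate: 1 − Φ[(threshold − m) / SD of change]. This is also the HOPE rate if HOPE adds nothing.
- HOPE rate with the plan's effect: the same, with m + .60 in place of m.

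**Results** (differences taken before rounding):

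| Reliability | r | PCT change (SD) | PCT rate | HOPE rate | Difference (points) |
|---|---|---|---|---|---|
| .9 | .55 | 0 | 17.8% | 38.6% | 20.7 |
| .9 | .55 | .3 | 27.2% | 51.0% | 23.8 |
| .9 | .55 | .6 | 38.6% | 63.3% | 24.7 |
| .9 | .55 | 1.0 | 55.2% | 77.7% | 22.5 |
| .8 | .7 | 0 | 5.5% (lowest) | 20.4% | 15.0 |
| .9 | .7 | 1.0 | 56.3% (highest) | 82.5% | 26.2 |
| .8 | .3 | 0 | 14.7% | 29.4% | 14.7 (smallest) |
| .9 | .7 | .6 | 36.1% | 66.2% | 30.1 (largest) |

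Over the whole grid, a HOPE arm that adds nothing would show reliable change in about 6 to 56% of women. The plan's effect would appear as a difference of about 15 to 30 points.

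The first and third rows show the difficulty. A HOPE rate of 38.6% arises when HOPE adds .60 SD and PCT women do not improve. It also arises when HOPE adds nothing and both arms improve by .6 SD. The HOPE rate alone cannot tell these apart; the PCT rate can (17.8% against 38.6%).

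**Precision of the between-arm difference.** Take 75 evaluable women per arm (150/2) and the third row. The standard error is √[(.386 × .614 + .633 × .367)/75] = .079, so the 95% interval is 24.7 ± 15.5 points, about 9 to 40. Across the grid, power to compare the two rates is 58 to 97%. The difference is informative as a supplementary estimate, though not always well powered as a test. These figures ignore shelter effects.

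**The case against.** The strongest reply is that the arm restriction is only inferred. The words that order the computation name outcomes and a time point, not an arm, and C3 requires every analysis to include all randomized women. This stands in part. A reader might infer that the index will be computed in HOPE alone, and the documents do not say so. But the intent-to-treat sentence fixes who is analysed, in contrast to the minimal attendance set. It does not create a comparison, and the stated question still concerns HOPE women.

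A reader might also infer that HOPE's contribution could not be separated from nonspecific change. That is not supported. The trial randomizes 93 women to each arm, and the same instruments are scheduled in both arms at that visit under blinded assessment.

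Nor is the efficacy conclusion compromised. It rests on the between-arm model, and the index is introduced as an addition with a descriptive aim. That model compares trajectories, however, and does not say how many more women improve reliably.

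It would be too strong to call the index the plan's only measure of clinical meaning. CAPS diagnostic status is collected at all major time points, and the VR-12, scored in QALYs, is a secondary outcome with its own two-group model. C3 does not name an analysis of diagnostic status, so the index remains the only responder-type analysis named there.

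Finally, uncontrolled improvement may be modest. Pilot symptoms had lasted nearly 38 months on average, and 83% of the pilot sample reported further IPV, contact with the abuser or another significant trauma after shelter. That is fair, and it is why the grid starts at no PCT improvement. The size is unknown in advance, which is itself a reason to report the PCT rate.

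**Conclusion.** The point holds as a gap in specification. The index is tied to change in HOPE participants and no contrast with PCT is planned, so followed as worded it yields an uncontrolled responder rate. The numerical ranges above are illustrations. Only the .60 SD comes from the plan; reliability, correlation, PCT change and the normal model are assumptions. The qualitative result does not depend on the exact values: at every point on the grid, some women in a HOPE arm with no added effect would be counted as reliably improved. The primary test, the sample size and data collection are unaffected, so this is an inexpensive improvement and not a threat to the trial's main conclusion.

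**What to change.** Replace the purpose clause in C3 with a between-arm specification:

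- Compute the index for CAPS PTSD severity in both arms at 1-week post-treatment, on the intent-to-treat imputed data, using one threshold for both arms and stating the reliability and SD behind it.
- Classify women within each imputed data set and pool the results.
- Report the proportions with reliable improvement and with reliable worsening in HOPE and in PCT.
- Give the between-arm difference with a 95% confidence interval, and make it the basis for any statement on clinically meaningful benefit of HOPE.

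The cost is a few lines in the plan. No visit, instrument or participant is added, because the CAPS is already scheduled in both arms at that visit. Writing it down before the data are seen also removes any choice of presentation afterwards.
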